3.1.1. Category I

- Subjects should have not received any collagenase treatments since the completion of the double-blind study.
- Subjects in which the maximum composite response was ONLY a 1-level composite improvement in cellulite severity at Day 71 as assessed by the PR-PCSS and CR-PCSS in either (or both) buttock(s) in the double-blind study. In cases where improvement was in both buttocks, the composite improvement of 1-level must have occurred in the same buttock (ie, the PR-PCSS and CR-PCSS improvement observed in the same buttock).
- Subjects who showed a 2-level improvement in one scale but only a 1-level improvement in the other scale, provided the composite improvement of 1-level was within the same buttock.
- Only buttocks with a composite 1-level improvement or less will be retreated.

- These subjects will be observed for time to reduction of response (defined in section 4.4.1) and safety approximately every 6 months for 2 years and will be observed annually for up to 3 years (Day 1080) from Day 71 of the double-blind study.

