3.8.2.1. Patient Reported Photonumeric Cellulite Severity Scale (PR-PCSS)

The subjects will rate the severity of the cellulite using the PR-PCSS for each buttock at Screening, and at the beginning of each visit where digital photography will be performed.

The PR-PCSS is a photonumeric scale ranging from 0 to 4 as mentioned in Table 6 below:

Table 6: PR-PCSS for Buttock

Severity Grade	Severity Labels	Description
0	None	No evident cellulite
1	Almost None	A few superficial dimples or ridges
2	Mild	Several dimples or ridges of which most are superficial
3	Moderate	Many dimples or ridges of which most are somewhat deep
4	Severe	A lot of dimples or ridges of which many are deep covering most of the skin area

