3.8.2.2. Clinician Reported Photonumeric Cellulite Severity Scale (CR-PCSS)

The Investigator will rate the severity of the cellulite using the CR-PCSS for each buttock at Screening, and at the beginning of each visit after the subject has completed her self-assessment using the PR-PCSS.

The CR-PCSS is a photonumeric scale ranging from 0 to 4 as mentioned in Table 7 below:

Table 7: CR-PCSS for Buttock

Severity Grade	Severity Labels	Description
0	None	No dimples or evident cellulite
1	Almost None	Few dimples that are mostly superficial in depth
2	Mild	Several dimples of which most are shallow in depth
3	Moderate	Many dimples of which most are moderate in depth
4	Severe	A lot of dimples with some of more severe depth

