2-level Composite Reduction	Worsening of cellulite severity improvement by at least 2-level on both PR-PCSS and CR-PCSS ratings compared to the score at Day 71/EOS (or Day 1) in the double-blind study.	Worsening of cellulite severity improvement by at least 2-level on both PR-PCSS and CR-PCSS ratings compared to the score at Day 71/End of Treatment Session in the open-label treatment phase.
1-level Composite Reduction	Worsening of cellulite severity improvement by only 1-level on both PR-PCSS and CR-PCSS ratings compared to the score at Day 71/EOS (or Day 1) in the double-blind study.	Worsening of cellulite severity improvement by only 1-level on both PR-PCSS and CR-PCSS ratings compared to the score at Day 71/End of Treatment Session in the open-label treatment phase.
Time to Composite Reduction of Response by 2-level	Number of days from the time of assessing composite improvement in cellulite severity on PR-PCSS and CR-PCSS at Day 71/EOS (or Day 1) in the double-blind study to the study visit prior to retreatment at which at least 2 level of worsening of response in both PR-PCSS and CR-PCSS ratings is observed for the first time.	Number of days from the time of assessing composite improvement in cellulite severity on PR-PCSS and CR-PCSS at Day 71/End of Treatment Session in the open-label treatment phase to the study visit during observation phase after retreatment at which at least 2 level of worsening of response in both PR-PCSS and CR-PCSS ratings is observed for the first time.
Time to Composite Reduction of Response by 1-level	Number of days from the time of assessing composite improvement in cellulite severity on PR-PCSS and CR-PCSS at Day 71/EOS (or Day 1) in the double-blind study to the study visit prior to retreatment at which only 1-level of worsening of response in both PR-PCSS and CR-PCSS ratings is observed for the first time.	Number of days from the time of assessing composite improvement in cellulite severity on PR-PCSS and CR-PCSS at Day 71/End of Treatment Session in the open-label treatment phase to the study visit during observation phase after retreatment at which only 1-level of worsening of response in both PR-PCSS and CR-PCSS ratings is observed for the first time.

Table 13: Reduction of Response (Continued)

Variables	Prior to Retreatment (including Through Day 180 Observational Period)	After Retreatment

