Baseline for Reduction of response and Improvement in Cellulite Severity (CR-PCSS and PR-PCSS)	
Improvement in Cellulite Severity: The assessment performed at Day 1 during the retreatment phase will be used as baseline to evaluate improvement in cellulite severity at Day 71 in this study.
 
Reduction of Response Prior to Retreatment: The assessment performed at Day 71/EOS visit in the double-blind phase will be used as baseline to evaluate reduction of response for any visits prior to/on first dose date of retreatment in this study.
 
Reduction of Response After Retreatment: The assessment performed at Day 71/End of treatment Session in the retreatment phase will be used as baseline to evaluate reduction of response during the observation phase after retreatment.

Baseline for CR-PCSS, PR-PCSS and PR-CIS Score	
At 180 Day Evaluation: The Screening assessment done within 14 days of Day 71/EOS of double-blind period will be used as baseline for 180 Day Evaluation period.
 
Before Retreatment: The Screening assessment done within 14 days of Day 71/EOS of double-blind period will be used as baseline for open-label period for subjects in TRR population who are not retreated, and until the point prior to retreatment for the subjects who are retreated.
 
After Retreatment: The assessments at Screening B/unscheduled assessment or Day 1 of the retreatment phase prior to/on the first dose date of retreatment in this study will be used as baseline.

Baseline for S-GAIS and Subject Satisfaction with Cellulite Treatment	The pretreatment Day 1 digital images from the double-blind study (EN3835-302/303) will be used as baseline.
Change from Baseline	Change from baseline will be derived as, post-baseline visit/time point value – the baseline value.
Time to reduction of response prior to retreatment (duration in days)	Date of visit where reduction is detected first – Date of Day 71/EOS of double-blinded studies 302/303
Time to reduction of response after retreatment (duration in days)	Date of visit where reduction is detected first – Date of Day 71/End of Treatment Session of open-label retreatment phase
Time to Complete Loss of Response prior to retreatment (duration in days)	Date of visit where complete loss of response reduction is detected first – Date of Day 71 of double-blinded studies 302/303 OR Date of Day 71/End of Treatment Session of open-label retreatment phase

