7.6.2. Reduction of response using PR-PCSS and CR-PCSS Prior to Retreatment

The proportion of subjects or buttocks with reduction of response (refer to section 4.4.1) will be summarized using frequency counts and percentages using TRR Population Before Retreatment and OLNLR Population subject category (ie, Category I and II, and Overall) and treatment area (ie, left and/or buttock) at the following visits prior to retreatment: Day 180, Month 12, 18, 24, and 36 where reduction of response is assessed.

The proportions will be computed based upon number of subjects within each category and treatment area remains not-retreated prior to that visit.

The following efficacy end points for reduction of response will be summarized:

- Proportion of subjects with 2-level composite reduction
- Proportion of subjects with 1-level composite reduction
- Proportion of subjects with complete loss of response

The time to composite reduction of response (ie, by 1-level and 2-level separately) and time to complete loss of response (refer to section 4.4.1 for derivation) will be summarized descriptively using TRR Population Before Retreatment and OLNLR Population.

The listings of cellulite PR-PCSS and CR-PCSS severity ratings will be provided for All Subjects prior to retreatment.

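### Prior to retreatment, 2-level composite reduction does not measure loss of a 1-level response, yet 1-level responders stay in its denominator and in the Overall figure

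*SAP*

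**What the plan says.** Both severity scales have five grades: "The PR-PCSS is a photonumeric scale ranging from 0 to 4" (3.8.2.1) and "The CR-PCSS is a photonumeric scale ranging from 0 to 4" (3.8.2.2).

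Section 3.1.1 defines Category I as "Subjects in which the maximum composite response was ONLY a 1-level composite improvement in cellulite severity at Day 71". It also admits "Subjects who showed a 2-level improvement in one scale but only a 1-level improvement in the other scale", provided the 1-level composite improvement is in the same buttock. Category II (3.1.2) needs at least 2 levels on both scales in at least one buttock.

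For the period before retreatment, Table 13 in section 4.4.2 defines the 2-level composite reduction as "Worsening of cellulite severity improvement by at least 2-level on both PR-PCSS and CR-PCSS ratings compared to the score at Day 71/EOS", with Day 1 given as an alternative reference in brackets. Table 17 (section 6.2) settles the reference: "The assessment performed at Day 71/EOS visit in the double-blind phase will be used as baseline to evaluate reduction of response".

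Section 7.6.2 then lists "Proportion of subjects with 2-level composite reduction" beside 1-level composite reduction and complete loss of response, by Category I, Category II and Overall and by buttock. The denominator is everyone in the category and treatment area not yet retreated before the visit. The time to 2-level reduction is summarised in the same population. Table 16 says reduction will be evaluated separately for subjects with at least 1-level and with 2-level improvement, but it does not tie the 2-level reduction endpoint to the 2-level responders.

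**The concern.** A buttock that gained one level has one level to lose before it is back where it started. An endpoint that asks for two levels of loss on both scales therefore does not describe loss of that response. It describes deterioration beyond the pre-treatment state on at least one scale and, for some starting scores, it cannot occur.

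Time to reduction of response is the only secondary objective (section 2.2). A low 2-level figure in the Category I row would partly reflect the definition. The Overall figure mixes buttocks that can lose a 2-level response with buttocks that never had one. The time to 2-level reduction would likewise mix loss of a 2-level response with worsening past the pre-treatment score.

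**Working it through.** The SAP states no figure on this point, so there is none to reproduce. The check is algebra followed by a full count of score patterns.

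**Inputs.** Scores 0 to 4 on each scale (3.8.2.1, 3.8.2.2). The composite improvement of a buttock is the smaller of its two improvements (3.1.1). The event is worsening of at least 2 on both scales from double-blind Day 71 (Tables 13 and 17).

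**Algebra.** Let B be the Day 1 score on a scale that improved by exactly 1. Then Day 71 = B − 1, and the event needs a score of at least (B − 1) + 2 = B + 1. That is worse than Day 1, and it is off the scale if B = 4. A composite improvement of exactly 1 means that at least one scale is in this position. Under the bracketed Day 1 reference the event needs at least B + 2 on both scales, which is stricter still.

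**Count of patterns, any Day 1 score.**
- Pairs of Day 1 and Day 71 scores on one scale with improvement of at least 1: 1 + 2 + 3 + 4 = 10. With improvement of at least 2: 1 + 2 + 3 = 6.
- Composite improvement of exactly 1: 10² − 6² = 64 patterns. Composite improvement of at least 2: 6² = 36 patterns.
- Event impossible: some scale went from 4 to 3. This gives 10 + 10 − 1 = 19.
- Event possible, both scales must end worse than Day 1: 3 × 3 = 9.
- Event possible, exactly one scale must end worse than Day 1: 2 × 3 × 6 = 36.
- Event possible without exceeding Day 1 on either scale: 64 − 19 − 9 − 36 = 0.

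| Composite improvement at Day 71 | Patterns | Impossible | Worse than Day 1 on both | Worse than Day 1 on one | Reachable without exceeding Day 1 |
|---|---|---|---|---|---|
| Exactly 1 level | 64 | 19 | 9 | 36 | 0 |
| At least 2 levels | 36 | 0 | 0 | 0 | 36 |
| Exactly 1 level, Day 1 scores 3 or 4 (assumed) | 24 | 13 | 1 | 10 | 0 |

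**Effect on Overall.** Let s be the Category II share of the denominator, p2 the Category II rate and p1 the Category I rate. Overall = s × p2 + (1 − s) × p1, which is below p2 whenever p1 is below p2. The SAP gives none of these. Setting p1 = 0 as the limiting case, Overall = s × p2:

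| Assumed p2 | s = 20% | s = 40% | s = 60% |
|---|---|---|---|
| 10% | 2% | 4% | 6% |
| 20% | 4% | 8% | 12% |
| 30% | 6% | 12% | 18% |

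**Do the other rows cover 1-level responders?** Complete loss is a return to Day 1 or worse on both scales, so every 1-level responder can reach it. The 1-level composite reduction asks for only 1 level on both scales. Of the 64 patterns, 4 × 4 = 16 improved by 1 on both scales and 64 − 16 = 48 improved unequally. A buttock in one of those 48 that returns exactly to Day 1 has lost 1 level on one scale and at least 2 on the other. It meets neither the 1-level nor the 2-level composite definition, and complete loss alone captures it.

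**After retreatment.** The reference becomes open-label Day 71, while Category stays fixed by double-blind Day 71. A Category I buttock scored 4 at double-blind Day 1, 3 at double-blind Day 71 and retreatment Day 1, 1 at open-label Day 71 and later 3, on both scales, has lost 2 levels without exceeding either Day 1. What matters in 7.6.3 is the response to retreatment.

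**The case against.** The plan already separates much of this. Category I and Category II have their own columns, so the Category II rate can be read without Category I. Table 16 promises separate evaluation by response level. Complete loss and 1-level reduction are reported alongside, so loss of response in Category I is not hidden. Everything is descriptive, with no test or success criterion resting on the row. Worsening past the starting point can also be observed over three years and is legitimate to describe.

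Most of this stands, and it limits the harm. It does not remove 1-level responders from the 2-level denominator, from the Overall figure or from the time summary. The group with at least 1-level improvement in Table 16 also contains the 2-level responders.

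A reader might infer three stronger things, and the SAP supports none of them:
- That the Category I rate will be near zero. The event is possible in 45 of the 64 patterns. Patterns are not probabilities, and no score distribution is given.
- That both scales must end worse than Day 1. This is so in 9 of those 45 patterns; in the other 36 it is one scale.
- That the fault applies to Category I after retreatment as well. The example above shows that it does not follow Category there.

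**Conclusion.** The point holds for the period before retreatment. For a buttock with only a 1-level composite response, a 2-level composite reduction always means ending worse than double-blind Day 1 on at least one scale, and it is impossible in 19 of 64 score patterns. This follows from the definitions and does not depend on how the scores are distributed.

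The size of the effect on Overall does depend on figures that the SAP does not give. If 1-level responders contribute essentially no events, an assumed 20% Category II rate would appear as 4% to 12% Overall for Category II shares of 20% to 60%. Any events among them would narrow the gap. The misleading items are the 2-level row for 1-level responders, its Overall figure and the time to it. The plan's account of durability as a whole is not shown to be wrong.

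**What to change.** In 7.6.2, limit the 2-level composite reduction proportion, its Overall figure and the time to it to buttocks with at least a 2-level composite improvement at double-blind Day 71, and say so in the denominator rule. Define the limit by buttock, because a Category II subject may have reached 2 levels in one buttock only. For 1-level responders, name complete loss of response as the loss measure, with 1-level reduction beside it.

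In 7.6.3, apply the same limit by response level at open-label Day 71 relative to retreatment Day 1, not by Category.

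The cost is wording in section 7.6 and the matching table shells, with no new data. The 2-level denominator becomes smaller, and the Overall 2-level loss rate is likely to look less favourable. If worsening past Day 1 is of interest, it can be reported under its own label.

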2.2. Secondary Objective

The secondary objective of this study is to assess the time to reduction of response (TRR) to CCH in the treatment of EFP in adult women.

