4.4.2. Reduction / Improvement of Response in Cellulite Severity Scale (PR-PCSS and CR-PCSS)

Reduction of Response will be assessed separately for prior to retreatment (including Through Day 180 Observational Period) and after retreatment. Refer below Table 13 for definitions of reduction of response:

Table 13: Reduction of Response

Variables	Prior to Retreatment (including Through Day 180 Observational Period)	After Retreatment
Reduction of Response	Worsening of cellulite severity improvement on PR-PCSS or CR-PCSS ratings in this study prior to retreatment compared to the score at Day 71/EOS (or Day 1) in the double-blind study. This reduction is also referred as a Partial Loss of Response.	Worsening of cellulite severity improvement on PR-PCSS or CR-PCSS ratings during the observation phase after retreatment compared to the score at Day 71/End of Treatment Session in the open-label treatment phase.
2-level Reduction	Worsening of cellulite severity improvement at least by 2-level on PR-PCSS or CR-PCSS ratings in this study prior to retreatment, compared to the score at Day 71/EOS (or Day 1) in the double-blind study (ie, change from baseline PR-PCSS and/or CR-PCSS rating of 2, 3, or 4)	Worsening of cellulite severity improvement at least by 2-level on PR-PCSS or CR-PCSS ratings during the observation phase after retreatment compared to the score at Day 71/End of Treatment Session in the open-label treatment phase (ie, change from baseline PR-PCSS and/or CR-PCSS rating of 2, 3, or 4)
1-level Reduction	Worsening of cellulite severity improvement by only 1-level on PR-PCSS or CR-PCSS ratings in this study after retreatment compared to the score at Day 71/EOS (or Day 1) in the double-blind study (ie, change from baseline PR-PCSS and/or CR-PCSS rating of 1)	Worsening of cellulite severity improvement only by 1-level on PR-PCSS or CR-PCSS ratings during the observation phase after retreatment compared to the score at Day 71/End of Treatment Session in the open-label treatment phase (ie, change from baseline PR-PCSS and/or CR-PCSS rating of 1)
Composite Reduction	Composite Reduction will be assessed using both the subject PR-PCSS responder classification and investigator CR-PCSS responder, where both the scales have same level of reduction. If the classification is missing for 1 or both components (ie, the PR-PCSS component or the CR-PCSS component), then the composite responder classification is missing for that visit.	

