Complete Loss of Response	Worsening of cellulite severity improvement on PR-PCSS and CR-PCSS ratings in this study prior to retreatment compared to the score at Day 71/EOS in the double-blind studies, where cellulite severity returns to baseline levels of the double-blind studies (ie, Day 1 of the double-blind studies) or worse.	Worsening of cellulite severity improvement on PR-PCSS and CR-PCSS ratings compared to the score at Day 71/End of Treatment Session in the open-label treatment phase, where cellulite severity returns to baseline levels of the retreatment phase (ie, Day 1 of the open-label retreatment phase) or worse.
Time to Complete Loss of Response	Number of days from the time of assessing composite improvement in cellulite severity on PR-PCSS and CR-PCSS at Day 71/EOS in the double-blind study to the study visit prior to retreatment at which the complete loss of response in both PR-PCSS and CR-PCSS is observed.	Number of days from the time of assessing composite improvement in cellulite severity on PR-PCSS and CR-PCSS at Day 71/End of Treatment Session in the open-label treatment phase to the study visit during observation phase after retreatment at which the complete loss of response in both PR-PCSS and CR-PCSS is observed.
2-level Improvement	Improvement in cellulite severity at least by 2 levels on PR-PCSS or CR-PCSS ratings from Day 1 of double-blind study (ie, change from baseline PR-PCSS and/or CR-PCSS rating of -2, or -3).	Improvement in cellulite severity at least by 2 levels on PR-PCSS or CR-PCSS ratings after receiving the retreatments compared to the corresponding rating at Day 1 of the Treatment Session of this study (ie, change from baseline PR-PCSS and/or CR-PCSS rating of -2, or -3).
1-level Improvement	Improvement in cellulite severity at least by 1 levels on PR-PCSS or CR-PCSS ratings from Day 1 of double-blind study (ie, change from baseline PR-PCSS and/or CR-PCSS rating of -2, or -3).	Improvement in cellulite severity at least by 1 levels on PR-PCSS or CR-PCSS ratings after receiving the retreatments compared to the corresponding rating at Day 1 of the Treatment Session of this study (ie, change from baseline PR-PCSS and/or CR-PCSS rating of -2, or -3).

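### SAP Table 13 leaves worsening of 1 level on one scale and 2 or more on the other outside both composite reduction categories, and its Day 1 alternative conflicts with Table 17

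*SAP*

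**What the plan says.** Section 2.2 sets one secondary objective: "The secondary objective of this study is to assess the time to reduction of response (TRR) to CCH". The event definitions are in section 4.4.2, Table 13.

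- **Composite reduction in general** applies "where both the scales have same level of reduction".
- **2-level composite:** "Worsening of cellulite severity improvement by at least 2-level on both PR-PCSS and CR-PCSS ratings".
- **1-level composite, before retreatment:** "Worsening of cellulite severity improvement by only 1-level on both PR-PCSS and CR-PCSS ratings compared to the score at Day 71/EOS (or Day 1"), both days belonging to the double-blind study.
- **Time to 1-level composite reduction** ends at the visit "prior to retreatment at which only 1-level of worsening of response in both PR-PCSS and CR-PCSS ratings is observed for the first time".
- **Per-scale 1-level reduction** is pinned to an exact value: "ie, change from baseline PR-PCSS and/or CR-PCSS rating of 1".
- **Complete loss before retreatment** needs worsening on both scales, "where cellulite severity returns to baseline levels of the double-blind studies (ie, Day 1 of the double-blind studies) or worse".

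The After Retreatment column words the 1-level and 2-level composite rows the same way, but its reference is Day 71 of the retreatment phase, with no Day 1 alternative.

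Section 7.6.2 summarises three proportions before retreatment (2-level composite, 1-level composite, complete loss) at Day 180 and Months 12, 18, 24 and 36, together with "The time to composite reduction of response (ie, by 1-level and 2-level separately) and time to complete loss of response". Section 7.6.3 adds either-scale reduction, but only after retreatment.

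Table 17 (section 6.2) gives Day 71/EOS of the double-blind study as the only baseline for reduction before retreatment and as the only start date for the time variable.

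**The concern.** The 1-level rule means exactly 1 on both scales and the 2-level rule means 2 or more on both. A buttock that worsens on both scales by unequal amounts, with one of them a single level, falls between the two. It is worse than a 1-level event, yet it is recorded as no composite event.

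The SAP does not treat mixed patterns this way elsewhere. Section 3.1.1 counts a mixed 2/1 improvement as a 1-level composite response. Section 3.1.2 describes the reduction considered for Category II retreatment as at least 1 level on both scales. A visit can therefore meet the score part of section 3.1.2 and still not count as a composite reduction in the analysis.

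The Day 1 alternative is a second problem. Day 1 precedes treatment, so no improvement has been assessed at that point, and it cannot be a coherent origin for time to loss of that improvement. Table 13 gives no rule for choosing between the two days. Two programmers could derive different events and different times from the same data.

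At stake are the composite proportions and event times that serve the secondary objective.

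**Working it through.** No sample-size or power figure is attached to this point, so the check applies the definitions literally to every possible score pattern.

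**Step 1: worsening pairs.** Both scales run from 0 to 4 (Tables 6 and 7), so worsening on each can be 1 to 4 levels, giving 4 × 4 = 16 pairs.

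| Table 13 category | Pairs (PR, CR) | Count |
|---|---|---|
| 1-level composite | (1,1) | 1 |
| 2-level composite | both ≥ 2 (3 × 3) | 9 |
| Neither | (1,2) (1,3) (1,4) (2,1) (3,1) (4,1) | 6 |

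With worsening limited to 2 levels per scale, 2 of 4 pairs are in neither; limited to 3 levels, 4 of 9. This step needs no assumption beyond the scale range.

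**Step 2: can complete loss pick these up?** With a 2-level composite response, Day 71 is at least 2 below Day 1 on both scales, so returning to Day 1 on both needs worsening of at least 2 on both. A mixed pattern has worsening of only 1 on one scale, so it can never be complete loss.

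Example: Day 1 3/3, Day 71 1/1, visit PR 2 and CR 3. Worsening is 1 and 2. The 2-level response versus Day 1 is no longer held (improvement now 1 and 0), so the score part of section 3.1.2 is met. It is not 1-level, not 2-level, and not complete loss because PR is still below 3.

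**Step 3: score triples.** Assumption: Day 1 scores of 3–4, with 2–4 in square brackets. The SAP does not give this range. I enumerated all Day 1 / Day 71 / visit scores with at least 1 level of improvement on both scales at Day 71 and at least 1 level of worsening on both at the visit. These are unweighted counts of patterns per buttock, not subject rates.

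| | Total | 1-level | 2-level | Neither |
|---|---|---|---|---|
| All both-scale worsening | 361 [676] | 49 [81] | 144 [289] | 168 [306] |
| 2-level response at Day 71 and section 3.1.2 score rule met | 240 [384] | 16 [27] | 120 [195] | 104 [162] |

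Of the 168 [306] in neither, 58 [138] are in 1-level-response buttocks, of which 32 [78] are complete loss. The other 110 [168] are in 2-level-response buttocks, and none is complete loss.

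**Step 4: timing.** A buttock that goes directly to at least 2 levels worse on both scales produces no 1-level event at that visit, because 1-level means exactly 1. A mixed visit gives neither time. A later confirmation, Screening B or Treatment Visit 1 rating before the first retreatment dose may supply an event time if it shows a qualifying pattern. It adds nothing to the section 7.6.2 proportions, which use fixed visits.

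**Step 5: Day 1 as reference.** If worsening from Day 71 is 1 on a scale that had improved by at least 1, the visit score is at or below Day 1 on that scale. Every 1-level pattern therefore stops being a reduction, and every mixed pattern stops being a both-scale reduction. Reclassifying the same triples:

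| Against Day 71 | Against Day 1: 2-level | 1-level | mixed | no both-scale reduction |
|---|---|---|---|---|
| 1-level, 49 [81] | 0 | 0 | 0 | 49 [81] |
| Mixed, 168 [306] | 0 | 0 | 0 | 168 [306] |
| 2-level, 144 [289] | 0 [4] | 9 [25] | 0 [20] | 135 [240] |

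In total 49 + 168 + 135 = 352 of 361 [81 + 306 + 240 = 627 of 676] are no both-scale reduction against Day 1. Example of a shift: Day 1 3/3, Day 71 2/2, visit 4/4 is 2-level against Day 71 and 1-level against Day 1. The time origins differ by 71 − 1 = 70 nominal days.

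**The case against.** **The exclusion is stated consistently and can be programmed.** This is true within Table 13: the general composite row and the 1-level rows all demand the same level on both scales. The defect is what the rule produces. A larger loss is reported as no composite event, out of line with how sections 3.1.1 and 3.1.2 handle the same scales. Those sections govern category and eligibility rather than the endpoint, so they show inconsistency but do not supply the missing rule.

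**Table 13 has an umbrella row.** Its first row defines reduction as worsening on either scale, section 7.6.2 opens with reduction of response in general, and Table 17's time variable does not say composite. A mixed visit would meet that row. However, the endpoint list and the time sentence in section 7.6.2 name only composite reduction and complete loss, so before retreatment the umbrella row leads to no stated endpoint. After retreatment, the either-scale lines in section 7.6.3 do show the worsening.

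**The Day 1 wording may mean a supportive analysis.** Sections 4.4.1 and 7.6.1 plan change-from-Day-1 summaries. Table 16 mentions Day 1 or Day 71 for the not-retreated population, which section 7.6.2 also uses. Nothing says that Day 1 defines a secondary version of reduction, and Table 13's complete-loss row itself compares with, and counts from, Day 71/EOS alone. The point does argue for labelling a Day 1 comparison rather than losing it.

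**The counts depend on assumptions.** This stands. The Day 1 range is assumed, and patterns are unweighted. Table 13's improvement rows list changes only down to −3; capping Day 71 improvement at 3 levels gives 108 of 225 [224 of 484] in neither, and 64 of 140 [110 of 252] under the section 3.1.2 score rule. The shares barely move, but they remain pattern counts.

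**Conclusion.** Both parts hold. Six of the 16 both-scale worsening patterns belong to neither composite category, in both columns of Table 13. In the pre-retreatment column only, the reduction definitions and composite times carry a second reference and origin that Table 17 does not allow. The 6 of 16 rests only on the scale range; the triple counts rest on assumed Day 1 scores and equal weighting.

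The direction is clear: as written, composite loss of response can be understated. The amount cannot be derived, because the SAP gives no frequency of mixed worsening.

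The consequence is bounded. The endpoint is descriptive with no test, the primary safety and immunogenicity objectives are untouched, and the ratings on each scale are still tabulated (section 7.6.1) and listed. It should be fixed because it concerns the sole secondary objective and the correction is cheap.

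**What to change.** 1. In both columns of Table 13, define 1-level composite reduction as worsening of at least 1 level on both PR-PCSS and CR-PCSS in the same buttock, timed at the first such visit. Keep 2-level (at least 2 on both) as a nested subset. All 16 pairs are then covered.
2. If exclusive categories are preferred for continuity, define 1-level as at least 1 on both and not at least 2 on both. The split becomes 7 / 9 / 0 instead of 1 / 9 / 6. Either version closes the gap.
3. Reword the general composite row of Table 13 so that it no longer requires equal levels on the two scales.
4. Remove the Day 1 alternative from the pre-retreatment reduction definitions and times so that they agree with Table 17. Label any Day 1 comparison as a separate change-from-Day-1 display.
5. If the Day 180 or safety-update cutoff outputs (section 6.4) used the exact-1 rule, keep it as a supplementary row.

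The cost is SAP wording and programming, plus that one row if needed. Reported 1-level loss rates may rise and may differ from earlier outputs. This changes analysis definitions only; the retreatment eligibility rules are left as they are.
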